10.4.2 Analysis of Secondary Efficacy Outcomes

In addition to the simple descriptive analysis of outcome measures, including correlation among them, a series of secondary efficacy outcomes are evaluated. The analyses for the secondary efficacy outcomes are conducted with SAS[®] Software System Version 9. Some outcome measures may have substantial departure from normal distribution, even after transformation, in which case nonparametric methods may be considered; however, with a sample size of approximately 1,100, we anticipate this to be rare problem. As these analysis results are treated as supportive evidence (or lack thereof) of the ALB treatment effect rather than conclusive evidence, the significance of each test is determined at the two-sided alpha level of 0.01 in order to control nominally for inflation of Type I error. The details of the secondary outcomes analyses are provided in the Statistical Analysis Plan.

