7.2 Complications of Thrombolytic Therapy

Intracranial hemorrhage (ICH): ICH is a known complication of thrombolytic therapy. Symptomatic ICH was observed in one subject in the Albumin Phase I Trial. Among subjects who are treated with IV thrombolysis, symptomatic ICH occurs in about 6% of subjects. Thrombolytic-related ICH generally occurs in the first 6 hours after thrombolytic therapy. The acute management of intracranial hemorrhage consists of the following:

- Immediate discontinuation of thrombolysis.
- Consider administration of cryoprecipitate, fresh frozen plasma, and platelets; there is no proof, however, that this empiric therapy results in an altered outcome.
- Subjects who concomitantly receive cryoprecipitate, fresh frozen plasma, platelets and ALB may be at particular risk of developing volume overload. These subjects should be managed, as needed, with additional furosemide to prevent the development of acute respiratory failure due to pulmonary edema.

Systemic hemorrhage: Systemic hemorrhage is an uncommon complication of thrombolytic therapy, occurring in less than 0.5% of patients. ALB administration was not shown to be a predictor of systemic hemorrhage in the Albumin Phase I Trial. Management is similar to ICH, and precautions against volume overload should be taken as discussed in Section 7.1.

Orolingual angioedema: Orolingual angioedema is an uncommon complication of thrombolytic therapy, occurring in 1% or less of subjects treated with thrombolysis. There is no known relationship between ALB therapy and angioedema. Risk factors for angioedema include the premonitory use of ACE inhibitor, β -blockers, and fronto-insular infarction [59]. Management of orolingual angioedema varies by severity. Most angioedema is mild and does not require treatment. Management with antihistamines (50mg IV diphenhydramine and 50mg IV ranitidine) may suffice. For more severe cases, 50mg IV hydrocortisone may be administered. Racemic epinephrine is not advised with thrombolysis because of the potential risk of inducing intracerebral hemorrhage. Early consultation with anesthesia for airway management should be considered for more severe cases

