10.2.2 Secondary Outcomes

The following are outcome measures to be evaluated as supportive evidence (or lack thereof) of the ALB treatment effect: (1) mRS score at 3 months; (2) mRS score at 12 months; (3) NIHSS score at 24 hours; (4) NIHSS score at 3 months; (5) BI score at 3 months; (6) EuroQol scores at 3 months; (7) EuroQol scores at 12 months; (8) SSQOL at 3 months; (9) stroke-free status as assessed by QVSFS at 12 months; (10) ASPECTS score by CT scan at 24 (\pm 6) hours; (11) proportion of subjects who do not have symptomatic ICH within 24 (\pm 6) hours; and (12) cognition as assessed by Trailmaking A and B at 3 months. The specific treatment of each of these outcome measures is detailed in the Statistical Analysis Plan.

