10.2.3 Safety Outcomes

Several specific adverse events are monitored throughout the study (see Section 8.8). However, death from any cause within 30 (\pm 7) days of randomization is evaluated statistically during and at the end of the Trial. We propose to use the 30-day mortality as the primary safety outcome because of the observed differences between the treatment groups during that period in the Part 1 of

the ALIAS Trial. Furthermore, the causes of death during that period are suspected to be more related to the study treatment compared to deaths occurring post-30 days from randomization. Clearly, the seriousness of this event requires close monitoring; therefore, we plan to conduct frequent interim analyses of this outcome (see Section 10.7.2).

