10.4 Data Analyses

10.4.1 Analysis of Primary Efficacy Outcome

The primary analysis for the Trial is to test the hypothesis of superiority of ALB therapy over placebo in acute ischemic stroke subjects, adjusting for the effects of thrombolysis and stroke severity. The analysis model for the primary efficacy outcome is:

$$E(Y) = \alpha + \beta_1 x_1 + \beta_2 x_2 + \beta_3 x_3 + \beta_4 x_1 x_2, \quad (1)$$

where Y= primary clinical outcome (0=unfavorable, 1=favorable), β_i is the regression coefficient, x_1 = treatment assignment (0=saline, 1=ALB), x_2 = thrombolysis treatment (0=no, 1=yes), and x_3 = baseline NIHSS score. The last term on the right hand side of the equation represents the study drug by thrombolysis interaction effect.

We will first test the interaction term. If it is not statistically significant at $\alpha=0.10$ or if it is statistically significant but the interaction is quantitative (i.e., if study drug effect is in the same direction in both strata), then we will test:

$$\beta_1 = 0 \text{ vs } \beta_1 > 0,$$

using the model:

$$E(Y) = \alpha + \beta_1 X_1 + \beta_2 X_2 + \beta_3 X_3 . \quad (2)$$

Otherwise, the primary efficacy analysis will be based only on subjects who receive thrombolytic treatment using the model:

$$E(Y) = \alpha + \beta_1 X_1 + \beta_3 X_3 . \quad (3)$$

For this test, we anticipate approximately 880 subjects in the thrombolysis stratum based on the observed recruitment ratio of 4 thrombolysis subjects to every one non-thrombolysis subject who were enrolled in the Part 1 of the Trial. If this ratio holds in Part 2, we will have insufficient sample size to test the non-thrombolysis group with adequate power; however, the data will be evaluated as exploratory analysis.

The primary analysis of the main efficacy outcome (whether the interaction is significant or not) is tested using the generalized linear model with log link function. It is tested at the one-sided alpha level of 0.025. PROC GENMOD procedure of SAS[®] v9 is used to obtain the test statistics and the results [130]. In addition, relative benefit ratio of ALB compared to saline and its 95% confidence interval are calculated.

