10.5 Analysis Samples

As the primary analysis, all futility and efficacy outcome measures specified in Sections 10.2.1 and 10.2.2 are analyzed under the ITT principle. For the outcomes measured at 3 months, the ITT sample includes all subjects who are randomized regardless of whether they actually received the study drug (ALB or placebo), and regardless of whether or not they had a 3-month outcome assessments. If they are missing, their data are imputed. See Section 10.6 for handling of missing data.

As secondary analyses, the 3-month outcome assessments may be analyzed excluding those who are lost-to-follow-up (LTFU) only if the proportion of LTFU is greater than 5%. If it is less than 5%, we anticipate that the analysis results with the excluded sample will differ minimally from the ITT sample. We also anticipate the possibility, albeit very small, of subjects receiving the incorrect treatment. This is considered a major protocol violation (PV). Nevertheless, as a tertiary analysis of outcome measures, we will repeat the analysis using this “as treated” sample upon completion of the Trial.

Any randomized subjects who received at least 20% of their weight-based dose of the study drug are included in the safety analysis sample.

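### Symptomatic ICH, a harm, is judged as a secondary efficacy outcome at two-sided 0.01, which makes a moderate excess harder to declare and is a stricter harm criterion than the one used for death

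*Protocol*

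**What the plan says.** Protocol 10.2.2 gives twelve secondary outcomes. Item (11) is the "proportion of subjects who do not have symptomatic ICH within 24" (± 6) hours, so the harm is coded as its absence and placed beside the functional and quality-of-life measures.

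Protocol 10.5 confirms how the list is classed: "all futility and efficacy outcome measures specified in Sections 10.2.1 and 10.2.2 are analyzed under the ITT principle".

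Protocol 10.4.2 then sets one criterion for all of these outcomes: "the significance of each test is determined at the two-sided alpha level of 0.01 in order to control nominally for inflation of Type I error". It describes the results as "treated as supportive evidence (or lack thereof) of the ALB treatment effect rather than conclusive evidence" and leaves further detail to the SAP.

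Protocol 10.2.3 names all-cause death within 30 days as the primary safety outcome and the one evaluated statistically during and at the end of the trial. It refers to 8.8 for other adverse events. Section 8.8 lists symptomatic ICH among the events followed by treatment group by unblinded personnel and the DSMB, without a numerical limit. For death, 10.7.2 uses the lower limit of a one-sided 99% confidence interval for the relative risk.

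**The concern.** A strict alpha across many secondary efficacy outcomes protects against declaring a benefit that is not there. For a harm the costly error is the opposite one, failing to recognise a real excess, and lowering alpha from 0.05 to 0.01 makes that error more frequent. Symptomatic ICH falls under the strict level only because of where it is listed.

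The outcome matters here. By the protocol's own recruitment experience about four in five subjects receive thrombolysis, the setting in which symptomatic ICH is most expected. The 0.01 test is the only formal end-of-trial comparison of symptomatic ICH that the protocol fixes. At stake is whether a moderate excess is reported as a signal or as a non-significant secondary result.

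**Working it through.** **Inputs**
- 1,100 subjects randomized 1:1, so 550 per arm (Synopsis; 10.3).
- Two-sided alpha 0.01 (10.4.2), critical value 2.576. Comparator two-sided 0.05, critical value 1.960.
- Rate with thrombolysis: "Among subjects who are treated with IV thrombolysis, symptomatic ICH occurs in about 6% of subjects" (7.2).
- Mix: "observed recruitment ratio of 4 thrombolysis subjects to every one non-thrombolysis subject" (10.4.1).
- Rate without thrombolysis: not given. Assumed 0% to 1%.

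Blended control rate: 0.8 × 6% + 0.2 × 1% = 5.0% (4.8% if the non-thrombolysis rate is 0%).

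**The protocol's own harm criterion, reproduced.** The protocol states no power or detectable difference for symptomatic ICH. The comparable figure is the first row of Table 10.7.2: 3 against 12 deaths at about 50 per arm.
- SE of ln RR = √(1/3 − 1/50 + 1/12 − 1/50) = 0.614.
- Lower limit = exp(ln 4 − 2.326 × 0.614) = 0.960, against 0.959 printed.

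So the death guideline uses 2.326, which is 0.01 in the harm direction. Two-sided 0.01 for ICH is 0.005 in the harm direction.

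**Power for symptomatic ICH.** Normal approximation, with p₀ and p₁ the two rates and p̄ their mean:

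power = Φ{ [ (p₁ − p₀) − z·√(2p̄(1 − p̄)/n) ] / √( p₀(1 − p₀)/n + p₁(1 − p₁)/n ) }

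For 5% against 7.5%: p̄ = 0.0625 and both standard errors are about 0.0146.
- At 0.01: (0.025 − 2.576 × 0.0146)/0.0146 = −0.86, power 19%, missed 81%.
- At 0.05: (0.025 − 1.960 × 0.0146)/0.0146 = −0.25, power 40%, missed 60%.

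| Control rate | Excess | Power at 0.01 | Power at 0.05 |
|---|---|---|---|
| 5% | 1.5-fold | 19% | 40% |
| 5% | 1.75-fold | 45% | 69% |
| 5% | 2-fold | 72% | 88% |
| 6% | 1.5-fold | 25% | 47% |
| 6% | 1.75-fold | 55% | 78% |
| 6% | 2-fold | 82% | 94% |
| 3% | 1.5-fold | 10% | 26% |
| 3% | 2-fold | 43% | 67% |

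Exact binomial enumeration agrees: for 5% against 10% at 0.01 it gives 69% (Fisher) to 73% (pooled z). Power at 0.01 reaches 50% at a relative risk of 1.79 for a 5% control rate and 1.71 for 6%.

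**A result just short of the criterion: 28 against 49 events of 550 each**
- Pooled rate 77/1,100 = 0.07. SE = √(0.07 × 0.93 × 2/550) = 0.01539. z = (21/550)/0.01539 = 2.48, two-sided p = 0.013. Not significant at 0.01.
- RR = 49/28 = 1.75, ln RR = 0.5596, SE = √(1/28 − 1/550 + 1/49 − 1/550) = 0.2291. 95% CI = exp(0.5596 ± 1.96 × 0.2291) = 1.12 to 2.74.
- One-sided 99% lower limit, as used for death: exp(0.5596 − 2.326 × 0.2291) = 1.03, above 1.
- Risk difference 3.8 points, 95% upper limit 3.82 + 1.96 × 1.534 = 6.8 points.

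The same split would cross the limit that 10.7.2 applies to death, yet count as non-significant under 10.4.2.

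**The case against.** A reader might infer that even a large excess would most likely be missed, or would be read as no effect. The documents do not support that. At a control rate of 5% to 6% a doubling is detected 72% to 82% of the time at 0.01; a doubling is more likely missed than found only if the control rate is about 3% or lower. No section says that a non-significant ICH result means no excess, and 10.4.2 calls the secondary results supportive rather than conclusive.

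Other points against the concern:
- Symptomatic ICH is already handled as a safety event during the trial. Section 8.8 has it followed by arm, 10.7.3 sends monthly safety reports to the DSMB by group code, and the Medical Safety Monitors adjudicate it. This stands as mitigation, but it sets no numerical limit for ICH and does not govern the final analysis.
- The SAP may report intervals for this outcome. That cannot be judged here, so the absence of an interval from the protocol is not the point. The point is the criterion that the protocol does fix for each secondary test; an SAP that judged ICH otherwise would depart from it.
- Low event counts cause much of the weak power: at two-sided 0.05 a 1.5-fold excess is still missed 60% of the time. This is true, and is why the fix relies on an interval rather than on a different alpha alone.
- The 0.01 level is not confined to efficacy, since 10.4.3 uses a Type I error of 0.01 for death. But the death guideline is one-sided and is set for repeated looks (eleven rows in Table 10.7.2). No repeated testing of ICH is planned, yet its harm criterion is the stricter one.

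The argument does not extend to stroke-free status (item 9), which can reasonably be read as a benefit outcome.

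**Conclusion.** The concern holds in a limited form. The protocol places a harm in the secondary efficacy family and gives it a significance level designed for another purpose. The cost is largest for moderate excesses: for a 1.5-fold excess the chance of missing it rises from 60% to 81% at a 5% control rate, and from 53% to 75% at 6%.

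These figures assume 550 evaluable subjects per arm, an unadjusted comparison, the protocol's 6% applying to its own 24-hour definition, the 4:1 mix holding, and a rate of about 1% without thrombolysis. Lower control rates worsen the picture: at 3% a 1.5-fold excess is missed 90% of the time. The mismatch between the ICH and death criteria does not depend on any of these assumptions. This should be changed, but it does not threaten the primary analysis.

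**What to change.** - In 10.4.2, limit the two-sided 0.01 criterion to secondary efficacy outcomes.
- Move symptomatic ICH (item 11 only) from 10.2.2 to 10.2.3 and 10.4.3 as a safety outcome. Leave stroke-free status (item 9) where it is.
- Report the risk difference and relative risk with a two-sided 95% CI. Base any statement of no excess on the upper limit, giving the largest excess not excluded, and not on non-significance at 0.01.
- State the analysis set. Under 10.5 the move takes ICH from the ITT sample to the safety sample (at least 20% of the weight-based dose received), so say whether the ITT result is also shown.

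The cost is wording in 10.2.2, 10.2.3, 10.4.2 and 10.4.3, with no extra subjects or data. The downside is a two-sided false-alarm rate of 5% instead of 1% on this one outcome.

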10.4.3 Analysis of Safety Outcome

The Cox proportional hazards model is used to analyze time to death within 30 days from randomization. The analysis adjusts for the effects of thrombolysis treatment, age (continuous), and baseline NIHSS score (continuous). The sample size of 1,100 yields an anticipated maximum number of events of 170 based on the 3.5-year subject accrual time at, on average, 1 subject per day (which is the rate observed around the time of enrollment suspension of Part 1 of the Trial) under the Type I and II error probabilities of 0.01 and 0.10, respectively.

10.4.4 Meta Analysis

The effectiveness or lack thereof of ALB will be determined solely from the analysis of the ALIAS Trial Part 2 primary outcome data. Additionally, at the end of Part 2 of the trial, as exploratory analyses, data from Parts 1 and 2 of the Trial will be combined for meta analyses.

10.5 Analysis Samples

As the primary analysis, all futility and efficacy outcome measures specified in Sections 10.2.1 and 10.2.2 are analyzed under the ITT principle. For the outcomes measured at 3 months, the ITT sample includes all subjects who are randomized regardless of whether they actually received the study drug (ALB or placebo), and regardless of whether or not they had a 3-month outcome assessments. If they are missing, their data are imputed. See Section 10.6 for handling of missing data.

As secondary analyses, the 3-month outcome assessments may be analyzed excluding those who are lost-to-follow-up (LTFU) only if the proportion of LTFU is greater than 5%. If it is less than 5%, we anticipate that the analysis results with the excluded sample will differ minimally from the ITT sample. We also anticipate the possibility, albeit very small, of subjects receiving the incorrect treatment. This is considered a major protocol violation (PV). Nevertheless, as a tertiary analysis of outcome measures, we will repeat the analysis using this “as treated” sample upon completion of the Trial.

Any randomized subjects who received at least 20% of their weight-based dose of the study drug are included in the safety analysis sample.

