The primary intent of the study was to evaluate the safety of escalating intravenous ALB doses and infusion rates and to determine the maximum tolerated dose (MTD) of ALB in subjects with acute ischemic stroke. The MTD was considered to be the highest dose level at which, in the view of the study's internal-plus-external Safety Evaluation Committee (SEC), ALB therapy is tolerated without the occurrence of unacceptable cardiac or other serious adverse events. The dose tiers evaluated were: (1) 0.34 g ALB per kg body weight; (2) 0.68 g/kg; (3) 1.03 g/kg; (4) 1.37 g/kg; (5) 1.71 g/kg; and (6) 2.05 g/kg. These doses were chosen based upon our extensive preclinical data showing that ALB doses of 1.25, 2.00, and 2.50 g/kg were highly neuroprotective in a rat model focal cerebral ischemia produced by middle cerebral artery occlusion. [12, 13, 17]. Two subject subgroups were represented in the trial:

- 1) Subjects admitted within the 0-3 hour window after stroke onset who received IV thrombolysis as well as ALB.
- 2) Subjects admitted within 16 hours of stroke onset who received ALB but not thrombolysis (either because they entered outside of the 0-3 hour thrombolysis window, or because they failed to satisfy one of the other thrombolysis exclusion criteria.)

In the initial dose-escalation design, separate cohorts of ~6 thrombolysis and ~6 non- thrombolysis subjects were accrued at each dose-level, and the SEC was asked to adjudicate the thrombolysis and non- thrombolysis cohorts of each dose-tier separately and to render separate decisions. As the trial progressed, however, it became evident that the thrombolysis and non- thrombolysis cohorts did not differ in the proportion of adverse events encountered. After Tier IV, the design was altered eliminating the stratification of enrollment by thrombolysis use.

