The placebo solution consists of isotonic saline solution. As 25% human albumin is a yellowish-brown liquid and the saline-placebo solution is clear, masking cartons and other masking materials, such as opaque sheaths for the tubing, are used to maintain blinding. ALB and saline-placebo are packaged into identical alphanumerically encoded study drug kits consisting of the masked bottles and opaque sheathing to obscure their identity. To further maintain blinding, a staff nurse not involved in the ALIAS Trial will hang the IV study drug/placebo and eliminate dead-space fluid from the IV line prior to starting the infusion. Similarly, this individual, or another staff nurse not involved in the ALIAS Trial, also will remove the study drug/placebo materials after the infusion and discard them after dose verification. Two individuals not associated with the ALIAS Trial must complete the Dose Verification Form. One of the individuals enters the dose to be given and signs and dates the form; the second individual enters the amount of material remaining in the vial(s), if any, after the infusion. That person also signs and dates his/her entry, which is on the same form as the dose entry. The independent clinical research associate (monitor) will review the Dose Verification Form to check the subject identification number and the appropriate administration of the study drug/placebo dose.

Bottles of ALB/placebo are 500ml and 250ml in size, and each subject has one bottle of each size assigned to him/her. Some subjects require only the 500ml bottle, but for heavier subjects, the second bottle may be needed. The 500 ml bottle is ALWAYS administered first. Subjects randomized to the ALB arm of the Trial receive a dose of 2.0 g/kg body weight of 25% human albumin (Baxter); this corresponds to a volume of 8 ml/kg body weight. Subjects randomized to the placebo arm of the Trial receive a volume of 8 ml/kg body weight of isotonic saline. In any event, even for subjects weighing more than 206 lbs (93.75 kg), the maximum ALB or placebo volume to be administered is 750 ml per subject. These solutions are delivered by constant intravenous infusion over a period of 2 hours (+/- 15 mins.). Although there is a 2 hour infusion time, the priority is that the full dose of the ALB or placebo be administered to the subject.

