6.2.3 Intervention Discontinuation Evaluations

ALB infusion may be prematurely terminated if the subject exhibits an anaphylactic reaction or other adverse event thought to be related to ALB. Acute reactions to albumin therapy are rare and no such events occurred during the Albumin Phase 1 study. It is remotely possible that a transfusion reaction consisting of hypotension, urticaria and or laryngospasm in combination or as isolated symptoms may occur. Management of such events should be undertaken according to the best standard of care. Use of antihistamines, fluid and pressor agents and ACLS airway management may be required.

When a subject has been treated with thrombolysis, careful distinction should be made between reactions to thrombolysis and reactions to ALB. It is known that a small proportion (~1%) of stroke patients may suffer acute orolingual angioedema after thrombolysis treatment. This reaction occurs more commonly when patients are taking concurrent angiotensin converting enzyme inhibitors and when infarction involves the insula. (See Section 7.2) Rarely, subjects treated with thrombolysis may develop sudden isolated hypotension, possibly related to release of bradykinin induced by thrombolysis. Management is with volume replacement. Treatment with ALB in this setting may be protective. A call to the ALIAS Medical Monitor in this setting may be helpful.

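### The safety sample requires 20% of the dose, so an exposed subject whose infusion is stopped early for a suspected drug reaction is left out of the formal safety analysis

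*Protocol*

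**What the plan says.** Section 10.5 gives the only definition of the safety sample in the protocol: "Any randomized subjects who received at least 20% of their weight-based dose of the study drug are included in the safety analysis sample". The intent-to-treat rule in the same section is tied to the futility and efficacy outcomes of 10.2.1 and 10.2.2. The primary safety outcome, death within 30 days, is in 10.2.3 and is not named there.

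On early stopping, section 6.2.3 says: "ALB infusion may be prematurely terminated if the subject exhibits an anaphylactic reaction or other adverse event thought to be related to ALB". It then describes acute reactions as rare, with none in the Phase I study.

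On mortality, section 10.4.3 says: "The Cox proportional hazards model is used to analyze time to death within 30 days from randomization". It works from a sample size of 1,100 and names no analysis set. Section 10.7.2 monitors the same outcome after every 15 deaths and also names none.

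On exposure, section 5.1 says ALB subjects "receive a dose of 2.0 g/kg body weight of 25% human albumin", that "this corresponds to a volume of 8 ml/kg body weight", and that "These solutions are delivered by constant intravenous infusion over a period of 2 hours", with 15 minutes' tolerance either way.

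**The concern.** Membership of the safety sample depends on something that happens after randomization and that the drug can cause. Leaving out subjects who never received drug would be one thing. This rule leaves out subjects who did receive it, and the subjects most likely to have a very short infusion include those who reacted at once. A safety set exists to capture rare, early, serious reactions, and 10.5 gives no reason for a 20% cut.

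The second issue is the primary safety outcome. Section 10.2.3 chose 30-day death because of between-group differences seen in Part 1. For that outcome the protocol should leave no doubt about who is counted, yet the only safety set it defines is the dose-restricted one.

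**Working it through.** **1. The threshold as dose and time.** Inputs are from 5.1 and 10.5.
- Dose: 0.20 × 2.0 g/kg = 0.4 g/kg.
- Volume: 0.20 × 8 ml/kg = 1.6 ml/kg.
- Time at a constant rate: 0.20 × 120 min = 24 min. Over the permitted 105 to 135 min, 0.20 × 105 = 21 min and 0.20 × 135 = 27 min.

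These times apply up to 93.75 kg. Above that weight, "the maximum ALB or placebo volume to be administered is 750 ml per subject", and 10.5 does not say whether the 20% is taken before or after the cap. At 120 kg, 1.6 × 120 = 192 ml, which is 192/750 = 25.6% of what can be given.

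**2. Is this negligible exposure?** Section 2.2.1 says: "The dose tiers evaluated were: (1) 0.34 g ALB per kg body weight". That tier is 0.34/2.0 = 17% of the present dose. A subject could receive more albumin than the whole first Phase I tier, which was itself evaluated for safety, and still fall outside the sample.

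**3. What carries the dose limit and what does not.**
- With the limit: the safety analysis sample in 10.5.
- Without it: follow-up (6.3), recording of adverse and serious adverse events (8.4), independent review of serious events (8.5), aggregate reports to the monitoring board (8.7) and by-group monitoring of listed events (8.8).
- Under intent-to-treat: the secondary outcomes of 10.2.2, including symptomatic intracranial hemorrhage.
- Unstated: 30-day death in 10.4.3 and 10.7.2.

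**4. Which denominators does the mortality guideline use?** I reproduced Table 10.7.2 with n = N/2 per group, a and b deaths, and

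lower limit = exp{ ln(b/a) − 2.326 × √(1/a + 1/b − 2/n) }.

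- N = 100, 3 and 12 deaths, n = 50: ln 4 = 1.386; √(0.3333 + 0.0833 − 0.0400) = 0.614; lower limit = exp(1.386 − 1.428) = 0.959. The table gives 0.959.
- N = 1,100, 69 and 96 deaths, n = 550: ln 1.391 = 0.330; √(0.01449 + 0.01042 − 0.00364) = 0.1459; lower limit = exp(0.330 − 0.339) = 0.991. The table gives 0.991.

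All 11 rows agree to three decimals. The table is built on full group sizes, with no deduction for subjects below 20% of dose. That points to all randomized subjects, but the text does not say so.

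**5. How many subjects?** The documents give no figure. If between 0.5% and 5% of 1,100 subjects fell below the threshold for any reason (my assumption), that is about 6 to 55. For acute reactions alone, none in 82 Phase I subjects has a one-sided 95% upper limit of 1 − 0.05^(1/82) = 3.6%, or about 20 of 550 ALB subjects. This is a ceiling on reactions of any timing, from a study in which most subjects had lower doses. Only reactions that stop the infusion in its first fifth matter here.

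**The case against.** The strongest reply is that little is lost. The protocol calls acute reactions rare. The main harm it names is volume overload (7.1), which in Phase I appeared hours or days after administration (2.2.2), so most such subjects would have passed 20% of the dose. Infusions stopped later than that stay in the sample. All of this stands, and it limits the size of the problem. It does not justify the rule.

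Three stronger readings are tempting, and the documents do not support them.

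- A reader might infer that these subjects disappear from the trial's safety information. They do not. Their events are recorded, reviewed if serious and sent to the monitoring board, and the subjects are followed for 12 months. They are missing only from the formal safety sample.
- A reader might infer that the 20% rule breaks the 30-day mortality comparison, or that one excluded death could reverse a monitoring look. No section applies the 20% sample to that monitoring, and the table uses full denominators. Looks are triggered by counted deaths, so an uncounted death would shift the timing of a look. The relative risk is covariate-adjusted, and the board may decide regardless of the guideline.
- A reader might infer a demonstrated bias in favour of ALB. A true albumin reaction can occur only on albumin, so the mechanism has a plausible direction. But treatment is blinded, saline infusions can also be stopped on suspicion, and other causes of a short infusion have no known direction.

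**Conclusion.** The point holds as a defect in a stated rule. The safety sample selects on a post-randomization event that the drug can cause, and it excludes exposed subjects who received less than 0.4 g/kg, roughly those stopped within 24 minutes (21 to 27). The conversion to time assumes a constant rate and a weight at or below the cap.

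The number affected is unknown and may be small. For 30-day death the finding is narrower: the protocol does not name the sample, although its planning figures fit all randomized subjects. The statistical analysis plan was not available and may settle the mortality sample, but the 20% rule is already fixed in the protocol.

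**What to change.** - In 10.5, define the safety sample as all randomized subjects in whom any amount of study drug was started.
- In 10.4.3 and 10.7.2, state that 30-day mortality is analysed and monitored in all randomized subjects, in the group to which they were randomized. This also covers subjects whose kit was opened, which is the moment of randomization under 4.3.3, but whose infusion never began.
- If a minimum-dose analysis is wanted, keep it as a labelled sensitivity analysis and say whether the 20% is taken before or after the 750 ml cap.

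The cost is one sentence in 10.5 and a clause in each of the other two sections, with matching text in the statistical analysis plan. No new data are needed: 6.3 already follows every randomized subject whatever was infused, and the Dose Verification Form in 5.1 already records the intended dose and the amount left over.
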